## 1.2 Funding

This pilot study is part of the overall SHAPES Innovation Action, which has received funding from the European Union's Horizon 2020 research and innovation programme under grant agreements No. 857159. The funder has commissioned reports on the results of this pilot study (D6.4).

### *Committees and oversight*

This medicine control and optimisation pilot study is within Work Package (WP) 6 of the overall SHAPES Innovation Action. WP6 will hold meetings independently of this pilot study. Likewise, the parties involved in this pilot will be involved in other work packages within the SHAPES programme and fall outside the remit of this protocol.

### *Pilot Management Group*

The Pilot Management Group (PMG) will typically host a monthly meeting. Key attendees are the Chief Investigator, relevant project managers (MOIC/NHSCT), representatives from EU pilot sites. Other attendees e.g., technical partners, Sponsor representative, funder representative, WP6 leader may be invited at the discretion of the Chief Investigator. Attendance and action minutes will be recorded.

### *Other relevant committees*

- The General Assembly (GA) is the ultimate decision-making body of the SHAPES consortium.
- The Project Management Board (PMB) is the supervisory body for the execution of the Project, which shall report to and be accountable to the General Assembly.
- The Executive Management Team assists the PMB and the Coordinator. The Coordinator is the legal entity acting as the intermediary between the Parties and the Funding Authority.
- The Ethics Advisory Board (EAB) is a consultative body to help ensure and strengthen the robust ethical standards of the SHAPES project and to support the consortium on any ethical issues that may arise.

## 2. Introduction

### 2.1 Background and rationale

People who are aged 65 years and older account for more than one fifth (20.6%) of the population of the European Union [1]. By 2100, this proportion is projected to rise to almost a third (31.3%) of the EU population. Conversely, the proportion of EU citizens who describe themselves as being in 'good' or 'very good' health is falling and varies considerably between member states (ranges between 43.4% and 83.8%) [2]. Naturally, being in 'good health' is not only of value to the individual (better quality of life, improved wellbeing, greater social participation), but it is also important for societal and economic growth [2]. Thus, there is an imperative to keep people healthy and active as they age.

As age increases, however, so too does the prevalence of people living with long term conditions and subsequently, the number and complexity of treatment regimens to manage those conditions, also known as polypharmacy. Integrated care focuses on the needs of the recipient of care, rather than each condition in silos — coordinating diagnosis and treatment between different therapeutic areas and specialties, and between health sectors. The benefits of integrated care models are clear (improved outcomes, established chains of prevention, diagnosis, treatment and care across the system); still, the complexity of health and care systems in individual countries and regions adds to the challenge.

The location of care delivery will also need to adapt to implement a truly integrated care approach to healthcare — shifting routine care from hospitals to homes and the community. Home is a more comfortable and familiar setting for people and, as it has been the case during the COVID-19 pandemic, home is safer too. Individuals with chronic health conditions require regular and specialist care and support. Whereas much of this type of care can be delivered at home by community nurses, or allied health professionals, who coordinate with the individual's other clinicians, it is often not logistically or economically possible to provide such services to all those who need them. The use of information and communication technologies (eHealth) offers opportunities to support and enhance home care. With the right eHealth technology, changes in a patient's condition can be potentially recognised at an early stage and treatment can be quickly adjusted — resulting in better-managed conditions and fewer hospitalisations.

Health literacy and individual involvement will be key elements in the successful introduction of eHealth into the health and social care system. Citizens, including older individuals, must be seen as custodians of their own health [3], thus emerging technologies need to be both user-friendly and empowering.

Specifically designed ICT-based assistive technologies may be of great benefit to older individuals who are increasingly at risk of frailty pertaining to mobility, vision, hearing and cognitive performance. Developments in ICT-based home care, including ways of monitoring wellbeing and providing a secure home environment, as well as key emerging technologies on robotics and sensors open up the concept of 'Ambient Intelligence' and offer the potential for different environments (i.e., at home, in the street, during transportation,) to embed intelligence that helps with everyday life. To date, initiatives to achieve traction in this area have been modest, with experiments involving advanced ICT services supporting health and care through small-scale, localised initiatives.

The Smart & Healthy Ageing through People Engaging in Supportive Systems (SHAPES) Innovation Action intends to build, pilot and deploy a large-scale, EU-standardised open access platform. The

Page 10 of 31

This project has received funding from the European Union's Horizon 2020 research and innovation programme under grant agreement No 857159

integration of a broad range of technological, organisational, clinical, educational and societal solutions seeks to facilitate long-term healthy and active ageing and the maintenance of a high-quality standard of life. Mediated by technology, in-home and local community environments interact with health and care networks contributing to the reduction of costs, hospitalisations and institutional care.

SHAPES intends to build an interoperable Platform integrating smart digital solutions to collect and analyse older individuals' health, environmental and lifestyle information, identify their needs and provide personalised solutions that uphold the individuals' data protection and trust.

Standardisation, interoperability and scalability of the SHAPES Platform aims to increase efficiency gains in health and care delivery across Europe, bringing improved quality of life to older individuals, their families, caregivers and care service providers. SHAPES large-scale piloting campaign will engage over 2k older individuals in 15 pilot sites in 10 EU Member States, including six European Innovation Partnership on Active and Healthy Ageing (EIP on AHA) Reference Sites, and involving hundreds of key stakeholders. SHAPES multidisciplinary approach to large-scale piloting is reflected across seven themes that, together, provide a clear understanding of the reality of European health and care systems and enable the validation of cost-effective, interoperable and reliable innovations capable of effectively supporting healthy and independent living of older individuals both within and outside the home.

These seven themes are as follows:

Pilot Theme 1 Smart Living Environment for Active Ageing at Home

Pilot Theme 2: Improving In-Home and Community-based Care Services

Pilot Theme 3: Medicine Control and Optimisation

Pilot Theme 4: Psycho-social and Cognitive Stimulation Promoting Wellbeing

Pilot Theme 5: Caring for Older Individuals with Neurodegenerative Diseases

Pilot Theme 6: Physical Rehabilitation at Home

Pilot Theme 7: Cross-border Health Data Exchange Supporting Mobility and Accessibility for Older Individuals

The Medicines Optimisation Innovation Centre (MOIC), which is hosted by the Northern Health and Social Care Trust (NHSCT) in Northern Ireland. Northern Ireland is an EIP on AHA reference site and is dedicated to driving innovation in medicines use. The MOIC is leading Pilot Theme 3 of the SHAPES pilot: 'Medicine control and optimisation', wherein the SHAPES platform and selected digital solutions will be used to help participants self-monitor their health condition(s), physiological parameters and medicines adherence. The anticipated benefits of this highly personalised approach to delivering healthcare is to promote safer and more effective use of medicines in the home, thus improving the health outcomes and quality of life of the target population [4]. Data collected from participants will provide validation of a heart failure decompensation algorithm which may, in future, be used to detect precursor signs indicating the deterioration or serious complications of the older individual's condition. Within this pilot theme there are multiple 'use cases' each deploying and evaluating different digital solutions according to the type of support required. Four use-cases will be used to evaluate this pilot theme. This protocol describes the piloting of one use case (Supporting multi-morbid older individuals) in NHSCT.

## 2.2 Hypothesis

This study will test the hypothesis that the SHAPES platform and Digital Solutions are capable of providing opportunities for supporting medicine control and optimisation in older people with multiple chronic health conditions.

## 2.3 Objectives

### *Primary objective*

- To investigate user engagement with the SHAPES app and Digital Solutions

### *Secondary objectives*

The following objectives are specific to the ‘Supporting multi-morbid older individuals’ use case:

- To validate the capability of the SHAPES platform and Digital Solutions to;
  - implement a personalised approach to achieve safe and effective use of medicines at home.
  - achieve better patient outcomes by initiating, developing and sharing best practice with regards to medicines use.
  - address and improve deficiencies with adherence to medicines and treatments.
  - identify associations between precursor signs of deterioration and unscheduled healthcare resource use.
  - improve data collection to develop predictive algorithms for heart failure decompensation.
  - improve older individuals’ quality of life.
- To explore the integration of the SHAPES platform and Digital Solutions to align with current and developing care pathways.
- To explore user trust and acceptance of the SHAPES platform and Digital Solutions.

### *Tertiary objectives*

The following objectives align with the general purposes of the SHAPES large-scale piloting campaign:

- To validate the capability of the SHAPES Platform and Digital Solutions to;
  - support and extend healthy and independent living for older individuals who are facing permanently or temporarily reduced functionality and capabilities.
  - improve the older individuals’ health outcomes and quality of life.

- gain the older individuals' trust and acceptance.
- gain the care professionals' trust and acceptance.
- contribute to the reduction of the workload of medical professionals.
- deliver efficiency gains in health and care delivery across Europe.

## 2.4 Pilot design

This is a non-randomised, single-armed, cross-sectional interventional pilot study with an optional qualitative interview component. The pilot will aim to recruit 30 participants who will be NHSCT service users.

Separate qualitative interviews will be held with up to 5 clinical leads employed by the Northern Health and Social Care service in Northern Ireland.

## 3. Methods

### 3.1 Study setting

The pilot will be conducted with service users from the Northern Health and Social Care Trust (NHSCT) who reside in their own home or supported living environment. Additionally, interviews will be conducted with clinical or policy leads in the NHSCT.

### 3.2 Eligibility criteria

#### *Service user inclusion criteria*

At point of consent;

- Northern Health and Social Care Trust service user
- ≥60 years
- Diagnosed with heart failure and/or diabetes mellitus
- If diagnosed with diabetes mellitus (and not heart failure), treatment includes regular monitoring of blood glucose
- Lives at home or in supported living accommodation (category 1 or 2).
  - Category 1 - self-contained accommodation for the more active elderly, which may include an element of scheme supervisor support and/or additional communal facilities
  - Category 2 - scheme supervisor supported self-contained accommodation for the less active elderly, which includes the full range of communal facilities
- Has stable self-reported Wi-Fi connection at home
- Has access to an appropriate android smartphone or tablet
  - Android device running version 6 or above; supports Wi-Fi; supports BLE; front facing camera for facial recognition
- Self-reported stable disease state, the participant feels well enough to take part in the pilot
- Self-reported confident user of smartphone/tablet

#### *Service user exclusion criterion*

At point of consent;

- Participant report of cognitive impairment
- Wears an electronic medical device or implant (e.g. pacemaker, electrocardiogram)
- Allergy to rubber products

#### *HSC staff inclusion criterion*

- Knowledge of patient care pathways
- Employed by the Northern Health and Social Care service in Northern Ireland

#### *HSC staff exclusion criteria*

- Unwilling or unable to provide consent

### **3.3 Intervention**

The intervention being piloted in this study is a novel system of supporting older individuals with multiple long-term conditions to self-manage their chronic conditions through the daily use of a digital health product that can also facilitate the remote monitoring of a person's health status.

The goals of the intervention are to help people self-monitor their health conditions, physiological parameters and medicines adherence to promote safer and more effective use of medicines in their own home. In future, the intervention will also facilitate the remote monitoring of people by health and social care practitioners and use artificial intelligence (AI) algorithms to predict deterioration in a person's health status. However, this functionality will not be investigated in the present study.

Participants will be asked to download the SHAPES app to an appropriate smartphone or tablet. Mock-up images of the app are provided as a supporting document. Four CE-marked, Bluetooth-enabled devices, specifically a body composition monitor (OMRON VIVA Smart Scale), glucometer (Roche Accu-chek Instant), blood pressure monitor (OMRON M7 Intelli IT) and pulse oximeter (Beurer GmbH PO60 Bluetooth pulse oximeter), will also be provided, as appropriate, to participants to use at home. Participants diagnosed with heart failure will be provided with the body composition monitor (OMRON VIVA Smart Scale), blood pressure monitor (OMRON M7 Intelli IT) and pulse oximeter (Beurer GmbH PO60 Bluetooth pulse oximeter). Participants diagnosed with diabetes will be provided with the glucometer (Roche Accu-chek Instant) and given the option to use the other devices according to preference. Participants will be encouraged to use the devices to take daily readings of their weight, blood pressure, heart rate and oxygen saturation, and readings of their blood glucose as per their existing diabetes care plan (if applicable). The readings are electronically transferred to the SHAPES app via Bluetooth. Participants can view their data via the app and have the ability to enter readings manually if required. Participants will also be encouraged to complete a daily survey containing questions about their health status (participants with heart failure only), and a weekly survey about their use of medicine. The participant's medication regimen will be uploaded to the app by researchers and will be available to view both as a comprehensive list of all medicines, and a daily list to serve as a reminder for what has to be taken that day. Participants will be asked via the app on a weekly basis if any changes had been made to their treatment that week so that their medication regimen can be amended accordingly.

Participants will receive one-on-one, face-to-face introduction to the app and training on how to use both it and the connected medical devices. A user manual will contain detailed step-by-step supportive guidance and information, and will be provided to participants in hard-copy format for reference by participants during the pilot. There will be a run-in period of approximately one week wherein the participant can familiarise themselves with the app and liaise with the researchers to troubleshoot any problems they may be experiencing with the technology. Participants will be asked to use the app and connected devices for 12 weeks. Researchers will contact participants by telephone at the end of week 1, if there are three or more consecutive days where no data has been received (up to a maximum of four times during the pilot) and monthly (if required) thereafter. These telephone contacts are to enable the researchers to support participants with their use of the technology and troubleshoot any issues they may be experiencing (no health advice or clinical support will be provided by the researchers. If participants have any health concerns they will be encouraged to contact their specialist care team).

All data entered or transferred into the SHAPES app (i.e., clinical readings, survey responses) is pseudonymised and will be stored in the technical partners' (EDGE and GNOMON) servers and then uploaded to the SHAPES big data platform. Selected data is then processed by two further SHAPES digital solutions; a heart failure decompensation risk prediction algorithm (VICOM) and an analytic tool that generates personalised dynamic thresholds for participants' clinical parameters (TREE). These digital solutions have not yet been validated or CE-marked for use as medical devices. Therefore, the outputs will not be used to inform clinical care, but rather to determine whether the digital solutions are capable of producing outputs reliably using the available data, and to indicate if there are any associations between the risk scores generated and the participants' use of unscheduled care.

Participants' data and outputs from VICOM and TREE digital solutions will be uploaded to a browser-based researcher dashboard. Researchers will be able to view each participant's clinical and survey data, and manage participants' medication regimens as needed. Researchers will view the available data and information for purposes of monitoring usage of the app and inputting changes to medication regimens only.

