| To validate the capability of the SHAPES platform and Digital Solutions to identify associations between precursor signs of deterioration and unscheduled healthcare resource use. | Correlation between HFPred scores and unscheduled care during the pilot
Association between HFPred scores and unscheduled care during the pilot (unscheduled care defined as composite of hospitalisations, A&E attendances, specialist contacts, out-of-hours contacts) | After pilot               |
| To validate the capability of the SHAPES platform and Digital Solutions to improve older individuals' quality of life  | EQ-5D-5L  | Baseline and end of pilot |
| To explore the integration of the SHAPES platform and Digital Solutions to align with current and developing care pathways.  | Exploration of healthcare practitioners' views on integration and alignment of the SHAPES platform and Digital Solutions with current care pathways   | During or after pilot     |
| To explore user trust and acceptance of the SHAPES platform and Digital Solutions.   | Exploration of participants' views about their trust and acceptance of the SHAPES app.  | End of pilot              |
|  | Exploration of user engagement behaviors  | After pilot               |

|   |   |  |
|---|---|--|
| To validate the capability of the SHAPES Platform and Digital Solutions to support and extend healthy and independent living for older individuals who are facing permanently or temporarily reduced functionality and capabilities | General Self-Efficacy Scale   | Baseline; End of pilot; 3-month follow-up  |
|   | Oslo Social Support Scale (OSSS-3)  | Baseline; End of pilot; 3-month follow-up  |
|   | Health literacy as measured using the Single-item Health Literacy Measure (HLM1)  | Baseline; End of pilot; 3-month follow-up  |
|   | Participation measure (non-validated)   | Baseline; End of pilot; 3-month follow-up  |
| To validate the capability of the SHAPES Platform and Digital Solutions to improve the older individuals' health outcomes and quality of life   | WHOQOL-BREF   | Baseline; End of pilot; 3-month follow-up  |
|   | EQ-5D-5L  | Baseline; End of pilot; 3-month follow-up  |
| To validate the capability of the SHAPES Platform and Digital Solutions to gain the older individuals' trust and acceptance   | System Usability Score  | End of pilot   |
|   | Technology Acceptance measure (non-validated)   | End of pilot   |

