##### *Service user baseline procedures*

- Questionnaires — Barthel Index, Gijon Scale, EHFS, MARS, BMQ, EQ-5D-5L, GSES, OSSS-3, HLM1, participation measure, WHOQOL-BREF
- Medical history data — height, weight, left ventricular ejection fraction, heart rhythm, implanted devices, medical conditions, heart failure stage, dyspnoea level, smoking status, leg pain symptom question
- Demographic data — including DOB, education, sex, marital status, occupational status, caregiver status, housing details
- Technical data — device monitoring details e.g. model, manufacturer, serial number and preferred time of day for reminders/questionnaires, make and model of the participants own smartphone/tablet
- Laboratory results — urea, creatinine, sodium, potassium, haemoglobin, cholesterol, eGFR, HbA1c, ACR, urine creatinine, urinary albumin-creatinine ratio
- Unscheduled care — hospitalisations (previous 3 months), and previous month hospital readmissions, A&E attendances, out of hours care, specialist service contacts, emergency ambulance call outs

- Current prescribed medication — name, frequency, strength, chronic or as required, stop date if stopped during the pilot, start date if started during the pilot.

*Service user study visits and procedures*

- During the pilot, the participant will be asked to record the following at least once daily, as appropriate, via the SHAPES app; blood pressure, heart rate, oxygen saturation, weight (which will include body mass index, body fat, visceral fat, skeletal muscle, basal metabolic rate).
- Participants diagnosed with diabetes and monitoring blood glucose regularly will be requested to record their blood glucose with the same frequency as directed by their doctor on the SHAPES app.
- Participants diagnosed with heart failure will be asked a series of daily questions about their heart failure symptoms administered via the SHAPES app.
- All participants will be asked about their adherence to medication with a weekly MARS questionnaire administered via the SHAPES app.
- During the pilot, the patient may view their medication list
- Unscheduled care updates — any updates to baseline hospitalisations, hospital readmissions, A&E attendances, out of hours care, specialist service contacts, emergency ambulance call outs recorded from medical notes
- Prescribed medication updates — any updates to prescribed medications notified by participant

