### 3.8.8 Missing data

Every effort will be made to reduce the potential for missing data, however, if missing data occurs it will be coded '999' or if applicable, the missing data protocol for the questionnaire or SHAPES protocol will be followed.

The VICOM heart failure prediction algorithm requires a number of data fields to be completed each day in order to provide a decompensation risk. If one of these values is missing, no risk prediction can be performed. It may be necessary on occasion to populate a participant's average value, e.g., if a participant is bed bound they will find it difficult to provide a daily weight value. These exceptions will be documented. If a complete data set is not obtained, data will be imputed. It will be clear to the researcher which risk scores are based on fully completed data versus partially completed and imputed data.

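### Researchers can see heart failure risk scores on the dashboard, and nothing keeps those scores apart from the recording of the unscheduled care they will be correlated with (minor)

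*Protocol*

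**What the plan says.** **Where the scores go.** Section 3.3 states that "outputs from VICOM and TREE digital solutions will be uploaded to a browser-based researcher dashboard". It then limits the use of the dashboard: "Researchers will view the available data and information for purposes of monitoring usage of the app and inputting changes to medication regimens only".

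**Whether scores are visible one by one.** Section 3.8.8 states: "It will be clear to the researcher which risk scores are based on fully completed data versus partially completed and imputed data".

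**What the scores are for.** Section 3.3 gives two aims for the algorithm outputs: to see whether they can be produced reliably, and to look for associations with unscheduled care. Section 3.4 makes the second a secondary outcome, and Table 1 lists it as "Association between HFPred scores and unscheduled care during the pilot". The composite consists of hospitalisations, A&E attendances, specialist contacts and out-of-hours contacts.

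**How unscheduled care is captured.** The in-pilot list in section 3.8.1 ends with "specialist service contacts, emergency ambulance call outs recorded from medical notes" and does not say who does the recording. The timeline table in section 3.5 puts unscheduled care updates in the row for data collected through the app.

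**How missing score inputs are handled.** Section 3.8.8 allows a participant's average value to be entered on occasion, with a bed-bound participant's weight as the example. It requires these exceptions to be documented.

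**The concern.** When a predictor is to be correlated with an outcome, whoever records the outcome should not know the predictor, and whoever completes the predictor should not know the outcome. Here both may pass through staff who can see both sides. A person who knows that a participant has high scores may search the notes harder, or count a doubtful contact that would be passed over in someone with low scores. A person who knows of an admission may be more or less ready to fill a missing input for that week.

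Either would distort the only listed outcome that relates the scores to clinical events. Section 2.1 says the data will help to validate the algorithm, so the result may be carried forward. Recording done with knowledge of the scores cannot be undone afterwards.

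**Working it through.** The protocol gives no figure to reproduce on this point, so the check sets its sections side by side.

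1. **Are score values open to researchers?** One sentence of 3.3, "Researchers will be able to view each participant's clinical and survey data", names clinical and survey data but not scores. The sentence before it puts the outputs on the dashboard, and 3.8.8 has the researcher distinguishing complete-data scores from imputed ones. Together these support visibility of individual scores. No date is given from which they appear. Section 3.8.6 has the research team using the portal throughout the pilot, so visibility during the pilot is the natural reading.

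2. **Do the stated purposes need the values?** Usage monitoring needs to know whether data arrived. Medication updates need the regimen and the participant's weekly reply. Neither needs a score. The study has two other uses for the scores: counting those generated per week (3.4) and telling complete from imputed ones (3.8.8). The first needs a count and the second a flag.

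3. **Who records events?** Section 3.8.1 does not say. Three statements point to the research team: it monitors data collection through the portal (3.8.6), clinicians have no access to the data collected (3.8.4), and only approved NHSCT and MEAAP project staff hold identifiable information (4.5). This remains an inference.

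4. **From what source?** Medical notes in 3.8.1, the app in 3.5. The difference matters here. If events come from notes, someone must read them and decide what to enter. If participants enter them in the app, the researcher has less discretion at capture.

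5. **Where is there room for judgement?**

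| Element | Room for judgement |
|---|---|
| Hospitalisations, A&E attendances | Little |
| Specialist and out-of-hours contacts | More |
| Value of a filled input | Little: 3.8.8 names the participant's own average |
| When to fill an input | Some: on occasion, with documentation but no masking |

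6. **Is there any separation?** No section masks the recorder to the scores, or holds scores back until events are recorded.

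7. **How large could the effect be?** It cannot be derived. The protocol gives no event rate, score distribution or misclassification rate. At most 30 participants contribute, so a few discretionary contacts could move a correlation, but the bias may also be nil.

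**The case against.** The case against giving this weight is substantial, and much of it stands.

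- **The recorder is not named.** A reader might infer that the team viewing the scores is the team abstracting the notes. The protocol does not say so. Sections 3.8.3 and 3.8.7 refer to a data plan for sources, and 3.8.10 to a Data Analysis Plan. Neither is shown, and either may settle who records and in what order data are locked. This stands, so the point cannot be stated as an established failure. The disagreement between 3.5 and 3.8.1 is, however, within the protocol itself.
- **Relatedness judgements do not enter.** A reader might think that deciding whether a contact relates to heart failure or diabetes could bias the association. In Table 1 that restriction belongs to the change-in-use and cost outcomes, not to the composite used with HFPred.
- **Telephone calls are not a route.** Sections 3.3 and 3.8.6 tie calls to the end of week 1, to gaps in data, or to monthly support. None is triggered by a score, and no health advice is given.
- **Scores should not drive care.** Section 3.3 keeps the outputs out of clinical care, and 3.8.4 denies clinicians the data. A reader should not infer that high scores lead to admissions.
- **Input filling is partly guarded.** The value is the participant's average, exceptions are logged, and complete-data scores can be analysed separately. Only the choice of when to fill remains open.
- **Hiding scores masks only in part.** Researchers would still see vital signs and symptom answers, from which deterioration can be guessed. This is a real limit on the remedy.

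What survives is that score values are exposed without a stated need, alongside some discretionary recording and filling.

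**Conclusion.** The point holds as a minor, optional improvement. The protocol shows score values to researchers beyond the viewing purposes it sets itself, and it states no separation between the scores and either the event record or the filling of inputs.

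The consequence is limited to one exploratory secondary outcome in a single-arm pilot of 30. Within that outcome it is limited mainly to specialist and out-of-hours contacts and to the choice of when to fill an input. The documents do not support a claim that the association will be inflated, or by how much.

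The conclusion rests on three assumptions: that the research team records unscheduled care, that scores are visible while recording is under way, and that the data plan does not already separate the two. If any of these is wrong, the remaining points are the unnamed recorder and the conflict over the source.

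**What to change.** In sections 3.3 and 3.8.1, with the timeline in 3.5 brought into line:

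1. Reconcile the source of unscheduled-care data (medical notes, app, or both with a stated order of precedence) and name who records it.
2. Complete and lock the unscheduled-care record and the log of populated inputs before HFPred score values are released to those staff and merged with the events.
3. Until the lock, show on the dashboard only a generated/not-generated count and the imputation flag. These serve the counting outcome and the distinction in 3.8.8.

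The cost is a display permission or a sequencing rule, plus a few sentences of text. No visits or measurements are added. Researchers lose sight of score values during the pilot. Masking stays partial because vital signs and symptom data remain visible for usage monitoring, so the lock before release does most of the work.
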